8.4 Procedures

i) Recruitment

Potential subjects will be identified by using the investigation sites' existing database of patients, or from Össur's customer database. Participants may be also recruited from external clinics and customers, through word of mouth, or during customer representative meetings where Össur representatives engage with users and clinicians. Customer representatives, who have prior experience interacting with and servicing patients, will evaluate if a potential participant is cognitively capable of participating in the study. Based on their assessment, the customer representative will inform the LPI of the potential subject and provide their contact information.

The LPI or PI will establish communication with potential participants and provide information about the investigation.

If a potential participant meets the inclusion and exclusion criteria, the LPI or the PI will contact them via telephone. During this call, the LPI or PI will:

- Verify the participant's interest in the study.
- Provide detailed information about the study and potential risk of participating in the investigation
- Answer questions related to the study.
- Conduct a preliminary screening to assess eligibility.

The LPI or PI will communicate to the study monitor the number of users he has identified that meet the inclusion criteria and are willing to participate.

ii) Test procedure

For **both phases**, at the beginning of the visit, a researcher qualified to obtain informed consent will explain the study to the subject and proceed as described in chapter 13.8 Informed consent.

The users will be fitted with the Power Knee device in a combination with an Össur foot. If the prescribed foot is an Össur foot, it will be used for the test. If the prescribed foot is not an Össur foot, then Pro-Flex LP will be provided for the test.

Configuration phase:

Both the current marketed firmware and the updated firmware will be optimally configured for each user.

This configuration will be carried out by the research engineers (Group 1), who will not participate in the evaluation phase to ensure blinding.

Randomization:

Once optimal configuration is achieved for both firmware versions, users will be randomized into two groups:

- Group A will start activity blocks with the current marketed firmware.
- Group B will start activity blocks with the Power Knee Firmware Update.

Evaluation phase:

For each activity block and according to the randomization, Firmware 1 (either the current marketed firmware or the updated firmware) will be uploaded to the device. Users will then perform the activity block.

Following this, Firmware 2 will be uploaded to the device. Users will repeat the same activities and tests performed with Firmware 1.

At the conclusion of each activity block, participants will complete a set of questions from the in-house questionnaire to evaluate and compare Firmware 1 and Firmware 2 in relation to the activity block they just performed.

This evaluation phase will be done by the other group of research engineers (group 2) who will be blinded. The upload of the firmware will be done by research engineers of the Group 1.

Activity blocks:

The order of the activity blocks is flexible, they can be applied in different sequences, and not all activity blocks need to be complete.

- Level-ground walking
- 10mWT
- Sit-to-stand
- 5XSTS
- Ramps
- Stairs
- Squatting
- 2-Minute Walk Test
- Pro-Flex Terra (For the phase I, they will perform the activity block using the last Firmware of the evaluation part (Firmware 2). For the phase II, they will perform these tasks with the updated firmware.)

Debriefing session:

After the testing session, a debriefing session will be organized, and all the research engineers will take part. The blindness will be removed for the users and the research engineers.

The activities are video recorded to visually compare the performance of the two firmware. Biomechanical data may be collected.

At the end they will be fitted back to their prescribed device. If the user has a Power Knee and if the user agrees, the current marketed version of the firmware will be uploaded to their devices if it was not already.

Phase I

The first phase will be used to assess the parameters defined in Table 4. Tasks performed include ADLs; Level ground, inclined, decline walking, stair ascent and descent, squatting, standing up and sitting down to a regular chair. Subjects will perform the 5XSST, 10mWT and 2MWT, see full description of functional tests in Annex 17.4. Subjects will be asked to provide feedback on the tasks tested with in-house questionnaires (see Annex 17.2 and 17.3) and open comments.

Phase II

The second phase is to validate the parameters defined in Table 4, this phase will include the same tasks and procedures as phase I with up to 30 amputee subjects.

In both phases, subjects will not be asked to carry out tasks they are not comfortable performing or that are considered too demanding.

iii) Measurements and data collection

Lasar Posture may be used to record prosthetic alignment.

The activities are video recorded to visually compare the performance of the two firmware and biomechanical data may be collected.

Inertial Measurements Units from Xsens¹⁵, may be used for measuring subject kinematics (including positions, angles, velocities and acceleration).

Moticon insoles¹⁶ may be used for measuring wireless pressure and acceleration during walking.

Optogait¹⁷ may be used for optical detection of the subject' movements, capturing space and time parameters for gait.

Microgate Witty Timing Gate¹⁸ may be used to measure speed and time of a subject walking between timing gates.

The activity report will be generated from the Power Knee software application and both from Össur Toolbox and Össur Logic.

Table 6 Visit schedule and procedures

		Recruitment phase: 2-6 weeks prior to baseline	Subject visit: baseline
Potential subjects identified, fitting inclusion/exclusion criteria, by LPI or PI from Össur customer database, other clinics, external customers		X	
LPI or PI will call potential subjects and screens by telephone		X	
Subjects will sign ICF			X
Subjects will be fitted with investigational device and prescribed foot			X
Configuration phase: Optimal configuration of both firmware			X
Subjects randomization			X
Evaluation phase	For each activity block:		X
	Subjects will have the Firmware 1 uploaded on the investigational device Group A: current marketed firmware Group B: updated firmware		
	Subjects will perform the activity block with the Firmware 1		
	Subjects will have the Firmware 2 uploaded on the investigational device Group A: updated firmware		

	Group B: current marketed firmware		
	Subjects will perform the activity block with the Firmware 2		
	Subjects will answer questions to compare Firmware 1 and 2		
Subjects will be fitted back to their prescribed devices			X
Debriefing session			X
If the subjects agree and if the users' devices do not have the latest version of the firmware, the research engineers will update the devices with the latest current marketed firmware			X
End of the study			X

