Instruments and equipment:	
Instruments :
 
 • In-house questionnaire with different activity blocks • 2MWT, 10mWT, 5XSST • Stair Assessment Index 
Equipment :
 
 • Investigational device : POWER KNEE Mainstream Firmware Update • POWER KNEE Mainstream, currently marketed as "POWER KNEE" • Pro-Flex Terra feet • Tools for fitting • Detailed protocol • Case report forms (CRFs); in Greenlight Guru – a tablet/computer or printout • Xsens, LASAR Posture, Moticon Insoles, Optogait, Microgate Witty Timing Gate 	
Subjects recruited:	Inclusion criteria:	Exclusion criteria:
Phase I: Up to 10 Phase II: Up to 30	50 kg < body weight < 116 kg	Users with pain*
	Lower limb loss, amputation or deficiency	Users with co-morbidities in the contralateral limb, which affect their functional mobility (except bilateral amputees)
	Cognitive ability to understand all instructions and questionnaires in the study	Users with osseointegrated prosthesis

	Transfemoral amputees	Users with cognitive impairment
	MPK users who use Power Knee or who tried Power Knee within the last 3 years	Pregnant users***
	Bilateral amputees	
	Hip disarticulation / Knee disarticulation amputees	
	Age \geq 18 years	
	Moderate to high active subjects	
	Willing and able to participate in the study and follow the protocol	
	Comfortable and stable socket fit**	
	No socket issues/changes in the last 6 weeks	

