A noticeable support of the swing phase in flexion and extension should be visible, plus a similar or an improved capacity at keeping up with the user in comparison to the current firmware. The dynamic of the swing phase while walking will be investigated via the 2MWT and 10mWT and potentially lead to similar or improved performance in comparison to the current firmware.

Concerning the sit-to-stand activities, time to perform the 5 times sit to stand test (5XSST) will be evaluated.

Similar as the previous tasks, stair ascent will be noticeable in the video documentation. In particular the subject will walk upstairs, stop and fully load the prosthetic knee. The time to perform the stair ascent will be documented and the performance will be evaluated with the Stair Assessment Index.

For each activity, the users will be asked to compare both firmware and rate on a worse, equal, better scale, if these tasks felt similar or different with the second firmware (without knowing which firmware is the updated one).

Additionally, feedback on the performance of the Pro-Flex Terra Foot and the POWER KNEE (phase I: with firmware 2, phase II: with updated firmware) will be collected.

The first phase can be repeated as many times as needed.

In phase II, the primary objective is to validate the firmware update.

The investigational device will be assessed with regards to its capability to be used with the indicated patient group, providing benefits to the subjects. No risks or anticipated adverse device effects (ADE) are to be assessed. The hypothesis and endpoints are specified in **Table 2**.

No claims are to be evaluated.

The following performance aspects are to be verified (relating to features in table 3 above):

- The investigational device provides perceived support to the user in sit to stand activities (Powered flexion and extension).
- The investigational device provides perceived support to the user in stand to sit activities (Controlled yielding).
- The investigational device provides natural speed adaptation within typical walking cadence, no perceived speed limit (Natural speed adaptation).
- The investigational device provides natural ambulation in stair ascent.

For all hypothesis:

μ_0 is average of measurements at baseline with the comparator (Power Knee with current marketed firmware);

μ_1 is the average of measurements with the investigational device (Power Knee with firmware update);

and $|M_{NI}|$ is the margin of non – inferiority

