8.1 General

The test will be a randomized, controlled, double-blinded, cross-over investigation for both phases I and II.

Amputees are a small proportion of the general population. The population group specified in the inclusion/exclusion criteria is a further subsample of amputees. For practical reasons, i.e. to achieve statistical power, it is therefore more feasible to use within-subject comparison rather than creating study arms to compare. The results of the phase I data collection will be used subsequent to first testing, to further improve the tested device, i.e. PKM. Furthermore, as mobile amputees generally have and use a prosthetic device for their daily activities, within-comparison is feasible comparing to the subjects previous device.

All investigational activities will be conducted at prosthetic out-patient clinics.

As stated above the primary endpoint is the general usability of the Power Knee Firmware Update in ADLs, which are specifically explained in the secondary endpoints are (see **Table 4**) in that respective order of significance. See previous chapter on objectives and hypothesis and **Table 4** for rationale.

Drop-outs and withdrawals may be replaced if deemed necessary to fulfil the methodological standards of the study.

Instruments for data collection will include the following:

2MWT: 2-minute walk test

10mWT: 10-meter walk test

5XSST: 5 times sit-to-stand test

Specific questionnaire: In-house generated questionnaire on specific features in the investigation device.

Video

Data logging by Ossur Logic/ Ossur Toolbox

See chapter **10.2 Sample size calculation**.

Equipment required for each subject:

- Detailed protocol
- Chair with Armrests for 5XSST
- Measuring tape
- Markers and a measure corridor/course of known distance for 2MWT and 10mWT
- Video camera for video documentation
- PC to read out Ossur Logic and Ossur Toolbox results
- Case report forms (CRFs) – Tablet/computer OR printed out case report forms
- Investigational device: POWER KNEE with the Firmware Update
- POWER KNEE with the current marketed firmware
- Pro-Flex Terra feet
- Other components as applicable (pylons and adapters for fitting)
- Tools for fitting
- LASAR Posture equipment for alignment
- Xsens (Annex 17.5.1)
- Moticon Insoles (Annex 17.5.2)

- Optogait (Annex 17.5.3)
- Microgate Witty Timing Gate (Annex 17.5.4)

The equipment used does not require specific monitoring, or maintenance.

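### One randomised firmware order per subject is reused in all eight two-firmware blocks, so identifying a firmware once can reveal the order in later blocks; redrawing the order per block is a cheap improvement.

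*Combined protocol and SAP*

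**What the plan says.** Section 8.1 calls the trial a "randomized, controlled, double-blinded, cross-over investigation for both phases I and II". Section 8.4 ii) sets the randomisation: "Once optimal configuration is achieved for both firmware versions, users will be randomized into two groups". The two groups are then defined: "Group A will start activity blocks with the current marketed firmware", and "Group B will start activity blocks with the Power Knee Firmware Update". The evaluation text carries this into each block: "For each activity block and according to the randomization, Firmware 1 (either the current marketed firmware or the updated firmware) will be uploaded to the" prosthesis, after which Firmware 2 is loaded and the block repeated. Tables 1 and 6 spell out the same order under the instruction for each activity block: marketed then updated for Group A, updated then marketed for Group B.

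Section 8.4 lists eight blocks that use both firmwares, plus the Pro-Flex Terra block, which has its own rule. After each block the user compares Firmware 1 with Firmware 2. Group 1 engineers configure and upload; Group 2 engineers run the evaluation blinded. Section 7 relies on the user judging "if these tasks felt similar or different with the second firmware (without knowing which firmware is the updated one"). The inclusion criteria in section 2 and Table 5 admit "MPK users who use Power Knee or who tried Power Knee within the last 3 years". Nothing provides for a new order per block, block-specific codes or a check of blinding.

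**The concern.** With two firmwares and one order per session, the first block's assignment determines the other seven. Someone who works out which firmware is which in one block, and who knows or guesses that the order does not change, carries that knowledge into blocks where the firmwares might otherwise be hard to tell apart.

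Recognition is plausible. Section 5 says the update changes the motor motion in sit-to-stand, the motor gains in swing, and stair ascent, and every user has worn a Power Knee. Group 2 staff watch both runs of each block.

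Hypotheses A1, A2, D, F, G and H are better/same/worse ratings used as phase II acceptance criteria, and they depend on the user not knowing which firmware is the update. E and I appear to be scored by an observer and depend on Group 2's blind. Session-wide labels also let a preference for Firmware 1 or 2 formed in one block carry into the next, so the rating rows are not fully separate comparisons.

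**Working it through.** **The plan's own figure.** Section 10.2 uses a null proportion of 0.6666 and g = 0.2834003, so p1 = 0.6666 + 0.2834003 = 0.9500003. For N = 15 and at least 14 successes, the exact binomial gives alpha 0.0193871 and power 0.8290491, as printed. Firmware order does not enter this calculation, so changing the order scheme leaves N and power as they are.

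**The acceptance rule.** Table 4 requires both P_worse < 0.333 and P_better > 0.333, each at p < 0.05. Exact one-sided critical values:
- n = 30: at most 5 'worse' (3.6% under the null) and at least 15 'better' (4.3%).
- n = 15: at most 1 'worse' (2.0%) and at least 9 'better' (3.1%).

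**Assumptions, none of them from the documents.** Each of the three changed functions reveals the order to a share r of users, independently. A user who knows the order and would have rated 'worse' changes the rating with probability h. There is no true difference between firmwares.

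**Share knowing the order at the third changed function, r = 0.3.**
- Fixed order: 1 − (1 − 0.3)^3 = 1 − 0.343 = 0.657.
- Redrawn per block: 0.30.

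**Biased P_worse = 0.333 × (1 − share × h), h = 0.3.**
- Fixed: 0.333 × (1 − 0.657 × 0.3) = 0.267.
- Redrawn: 0.333 × (1 − 0.30 × 0.3) = 0.303.

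If the rating moves to 'same', P_better stays at 0.333. If it moves to 'better', P_better rises by the amount that P_worse falls: to 0.399 (fixed) or 0.363 (redrawn).

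**Joint pass probability.** Sum the trinomial probability n!/(w! b! s!) × P_worse^w × P_better^b × P_same^s, with s = n − w − b, over all counts that meet both critical values.

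| r = h = 0.3 | Intact blind | Redrawn | Fixed |
|---|---|---|---|
| n = 30, 'worse' to 'same' | 0.9% | 1.3% | 2.0% |
| n = 30, 'worse' to 'better' | 0.9% | 2.3% | 6.2% |
| n = 15, 'worse' to 'same' | 0.4% | 0.6% | 0.8% |
| n = 15, 'worse' to 'better' | 0.4% | 0.9% | 2.1% |

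**Range at n = 30, fixed against redrawn.**
- 'Worse' to 'same': 1.36% against 1.05% at r = h = 0.2; 3.5% against 2.3% at r = h = 0.5.
- 'Worse' to 'better': 2.5% against 1.35% at r = h = 0.2; about 32% against 9.5% at r = h = 0.5.

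**A stronger bias.** If a share u of users knows the order and all of them rate the update 'better', then P_better = (1 − u)/3 + u and P_worse = (1 − u)/3. For u = 0, 10%, 20% and 30%, the joint pass rate is 0.9%, 4.0%, 11.6% and 24.6% at n = 30, and 0.4%, 1.5%, 3.8% and 8.1% at n = 15. This shows sensitivity to unblinding from any source; it is not itself a comparison of fixed with redrawn order.

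**The case against.** One randomised sequence per subject is how an ordinary crossover works, and redrawing per block is a refinement. That is fair as far as it goes, but an ordinary crossover makes one comparison per subject, whereas here the same sequence is used eight times in a session with a rating after each.

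Several limits stand.
- Feeling a difference is not the same as knowing which version is the update. Some users have only tried a Power Knee, and users' own devices may not carry the latest firmware.
- The documents do not say that users are told the order is constant.
- The contrast of 66% with 30% needs independent chances of recognition. If the same perceptive users recognise the firmware every time, fixed and redrawn orders give the same share. A user who has learned the update's feel may also identify it again under any order, so 30% is a best case for redrawing.

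Stronger inferences are tempting but not supported.
- A reader might take the P_worse test alone, which at n = 30 and r = h = 0.3 gives 14.8% fixed against 7.2% redrawn, as the false-validation rate. Table 4 requires the P_better test too, and under a 'worse' to 'same' shift that test holds the joint rate near 2%.
- A reader might take section 7 as saying that the plan expects recognition. The statement "A noticeable support of the swing phase in flexion and extension should be visible" describes swing support, and its explicit comparison with the current firmware is similar or improved capacity. The remark about stair ascent being noticeable refers to the video record. The changes listed in section 5 are the better evidence.
- Carry-over of a label preference correlates the rating rows, but across randomised groups it does not by itself favour the update.

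Section 14.3 says that allocation is visible. This does not answer the point: it contradicts sections 7, 8.1 and 8.4, and the passages must be reconciled.

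**Conclusion.** The structural weakness is real: one order per subject governs all eight two-firmware blocks, and one identification can spread to the later ones. It does not follow that the blinded ratings as a whole lose their protection. The loss is conditional on recognition and on realising that the order is constant, and it affects only ratings made afterwards.

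The size cannot be fixed from the documents, because they give neither a recognition rate nor the direction of any bias. At the central assumptions the fixed order costs little on the full Table 4 rule if informed users soften 'worse' to 'same', and takes it slightly above 5% at n = 30 if they switch to 'better'. Large inflation needs high recognition together with a shift to 'better', or a group of informed users who all favour the update. This supports a low-cost improvement to the design, not a finding that phase II validation would be invalid.

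**What to change.** In section 8.4 ii), Table 1 and Table 6:
- Replace the single Group A/B order with a firmware order drawn separately for each activity block, from a pre-generated list held by Group 1. Balance it across subjects within each block. Do not force balance within a subject: that would make late blocks partly predictable, and it could not be kept when block sequence is flexible and blocks may be skipped.
- Use labels that apply only within the block (first and second in this block).
- Perform an upload step before every run, even when the firmware does not change, so that a missing upload is not a cue.
- Log the version loaded for each run and store the block's order with each rating, so that the rating is coded as update versus current.
- The phase I Terra block and row J are defined by Firmware 2, which would lose its session-wide meaning. Define the Terra firmware in phase I as the one last loaded in the preceding block.

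Cost: protocol wording and a longer list. Group 1 already uploads firmware for each run, so no extra subjects, visits, staff or runs are needed, and the sample size is unchanged. The downside is a more complex upload list with some risk of loading or coding error, controlled by the log. Redrawing cannot prevent recognition by feel within a block; it limits how far recognition spreads.

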The device under investigation (the Investigational Device) is a **modification of a CE-marked** medical device currently marketed (Power Knee Mainstream). From now on in this document, the investigational device will be referred to as **POWER KNEE Mainstream Firmware Update**. The core component of the system is a motorized knee prosthesis along with other important parts which, are necessary for the device's operation, functionality and safety. More specifically, POWER KNEE Mainstream Firmware Update is composed of four parts. Besides the motorized knee itself one of these is a detachable battery pack providing the system with power and thereby making it operational as a motorized knee prosthesis. Another part is the prosthesis configuration device that allows adjustment of the knee parameters to optimize its performance with respect to the user physiological characteristics, activity level, gait style and personal preferences. Furthermore, with the battery pack comes an off-the-shelf power supply allowing recharging of the battery when not installed in the knee prosthesis.

POWER KNEE Mainstream Firmware Update is based on the concept and technology of the existing POWER KNEE MAINSTREAM which is commercially available, but the firmware has been updated to enhance functions of ADLs such sit to stand, level walking, and stair ascent. Hence some changes in the algorithm have been made:

The description of the modifications for the sit to stand, swing phase, and stair ascent are:

- Sit-to-stand: The change concerns the power delivery from the motor during standing up. The triggering will remain the same, but the motor motion will change.
- Swing phase: During the swing phase, the gains of the motor control changes based on the knee angle relative to the target flexion angle.
- Stair ascent: The stair ascent activity should be more fluid and in synchronization with the user.

See Table 2 for details on the investigational device.

Table 2 Identification and Description of the Investigational Device

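### Phase II visits end with a debriefing that unblinds the Group 2 evaluators before later subjects are tested, and the plan neither settles who scores E and I nor requires scoring to be finished first

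*Combined protocol and SAP*

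**What the plan says.** Section 8.1 declares the design: "The test will be a randomized, controlled, double-blinded, cross-over investigation for both phases I and II".

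Section 8.4 ii) divides the engineers to protect the blind. Group 1 configures both firmware versions and stays out of the evaluation. For the evaluation, "This evaluation phase will be done by the other group of research engineers (group 2) who will be blinded", while "The upload of the firmware will be done by research engineers of the Group 1".

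The same section then calls all research engineers to a debriefing after the testing session, where "The blindness will be removed for the users and the research engineers". Tables 1 and 6 both mark the item "Debriefing session" in the subject-visit column. Phase II repeats the Phase I tasks and procedures, and section 8.2 schedules two subjects per day.

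Other relevant text:

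- Section 5 says of sit-to-stand, "The triggering will remain the same, but the motor motion will change", and of stairs, "The stair ascent activity should be more fluid and in synchronization with the user".
- Section 8.4: "The activities are video recorded to visually compare the performance of the two firmware". No masked reader and no time of reading are given.
- Table 4, Phase II: E is the Stair Assessment Index with a 1-point margin. I, a secondary hypothesis, is a count of unexpected movements tested against zero. No scorer is named for either.
- Section 8.6 gives the local principal investigator (LPI) the conduct of all trial procedures at the site. It gives data collection to the LPI, the local co-investigator and the principal investigator.
- Section 13.9 h) limits sponsor representatives to observing during the procedures.
- Section 14.3 says that breaking the blind is not relevant because allocation can be seen.

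**The concern.** Each reveal pairs what Group 2 has just watched with a firmware label. Nothing in the supplied text postpones it to the end of Phase II, replaces evaluators after a debriefing, or requires scoring to be complete beforehand. The update is meant to move differently, so an evaluator who sees several reveals may come to recognise it in subjects whose sequence is still concealed. For video of a subject already debriefed, the sequence is known outright.

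At stake are the outcomes that appear to need an observer's judgement. A scoring shift towards the update uses up the 1-point margin of E. It acts directly on I, which has no margin to absorb it.

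Two further points weaken the declared blind. The Phase II Pro-Flex Terra block is performed with the updated firmware and block order is flexible, so the known update may be used before the blinded comparisons. And section 14.3 contradicts sections 8.1 and 8.4.

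**Working it through.** **1. Is the reveal per visit?** Tables 1 and 6 place the debriefing within the visit. Users attend one half-day session and are unblinded there. A single reveal at the end of the phase does not fit that text.

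**2. Which Phase II hypotheses are reached?** Table 4 gives acceptance criteria for 11 (A1, A2, B, C, D, E, F, G, H, I, J).

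- Seven (A1, A2, D, F, G, H, J) are user ratings, given at the end of each activity block and so before that user's debriefing.
- B and C are a measured time and distance.
- E and I remain: 2 of 11, plus any video scored after a debriefing. Video has no row of its own in Table 4.

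**3. Who scores?** Section 8.4 gives the evaluation to Group 2. Section 8.6 gives trial procedures and data collection to the LPI, the local co-investigator and the principal investigator, and does not list research engineers by that name. Section 13.9 h) has sponsor representatives only observe. The reveal names users and research engineers, so if site staff score E and I, its wording does not reach the scorer. The text does not settle this. Annex 17.4, which holds the test descriptions, was not available for this check.

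**4. How many subjects are exposed?** Assume one Group 2 team throughout. With sequential visits, N − 1 subjects are evaluated after at least one Phase II reveal: 15 − 1 = 14 of 15, or 30 − 1 = 29 of 30. If the two first-day subjects overlap, it is N − 2: 13 or 28. The values 15 and 30 are the minimum number of completers (sections 8.3 and 10.2) and the maximum enrolment (section 8.2). The plan's N = 15 reproduces from its inputs (critical value 14, null 0.6666, alternative 0.6666 + 0.2834 = 0.95): exact alpha 0.0194, power 0.829. It has no bearing on blinding.

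**5. What would a scoring shift do?** The plan gives no SD and no bias, so the shift is assumed. Let b be the mean shift towards the update among exposed subjects, in SDs of the paired difference. Averaged over all N it is b(N − 1)/N, so the noncentrality is b × (N − 1)/N × √N. The SD is taken as unchanged. Section 10.1 specifies a two-tailed paired t-test, at 0.05 in Table 4, so the error in the favourable direction without bias is 0.025. With bias it is P(T > t(0.975, N − 1)), where T is noncentral t.

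| N | critical t | b | b(N − 1)/N | noncentrality | favourable error |
|---|---|---|---|---|---|
| 15 | 2.145 | 0.10 | 0.0933 | 0.361 | 0.052 |
| 15 | 2.145 | 0.25 | 0.2333 | 0.904 | 0.132 |
| 30 | 2.045 | 0.10 | 0.0967 | 0.529 | 0.074 |
| 30 | 2.045 | 0.25 | 0.2417 | 1.324 | 0.248 |

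With N − 2 exposed, the errors are 0.050 and 0.120 at N = 15, and 0.071 and 0.235 at N = 30. For I they apply when there is no true difference. For E they apply only if the true difference lies exactly at the margin. The Wilcoxon alternative in section 10.1 was not computed.

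**The case against.** The harm needs a chain of conditions: the same engineers continue, they score E or I, the versions look different, the engineers learn this, and their scores move. The documents establish none of these links outright. The plan does not say that evaluators can tell the versions apart, and site staff may be the scorers. Table 4 lists sensor logging for E and cites very high reliability for the Stair Assessment Index, which may leave little room for a shift. I is secondary. Phase I reveals come first and Phase I may be repeated, so the same engineers might already know the update by Phase II.

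Most of this stands, and it is why the point is conditional and unquantified. Three things remain. Reliability between ratings does not show that scores resist a rater's expectations. The silence on who scores is itself a gap. And the contradiction between section 14.3 and sections 8.1 and 8.4 does not depend on the chain.

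A reader might infer more: that the debriefing discloses the next subject's order, or that it undermines every Phase II endpoint. Neither is supported. Each subject is randomised, so a reveal gives only that subject's sequence, and the ratings precede the user's own reveal. A reader might also conclude that the Terra block will be run early. It is listed last, its Phase I wording puts it after the evaluation part, and Phase II follows the same procedures. An early run is permitted, not planned.

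**Conclusion.** The concern holds in a limited form. Phase II is declared double-blinded with blinded Group 2 evaluators, yet each visit contains a reveal to all research engineers, and nothing in the supplied text defers it or requires prior scoring. The reach is at most E and I among 11 hypotheses, plus video scored after a debriefing, and only if those who attend the reveals go on to score. Under one continuing team, 14 of 15 or 29 of 30 subjects would be evaluated after a reveal.

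The size of any bias cannot be estimated from the documents. The error rates above show sensitivity to assumed shifts and should not be read as the trial's actual error. The inconsistency over who scores, and that between section 14.3 and the declared blinding, are matters of text and need correction in any case.

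**What to change.** 1. In Phase II, withhold the reveal from Group 2, and from anyone who scores E, I or video, until the last subject has been tested and these outcomes have been scored. Group 1, who already upload the firmware, can unblind the user without them.
2. Reconcile sections 8.4, 8.6 and 13.9 h) on who scores E and I, and name the scorer.
3. Place the Phase II Pro-Flex Terra block after all blinded comparison blocks.
4. Reconcile section 14.3 with sections 8.1 and 8.4.

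These are wording changes, with no added staff, visits or subjects. The downside is that Group 2 gets unblinded feedback only at the end of Phase II: up to three weeks on the stated phase duration, or three months on the stated enrolment period (both section 8.3). Phase I debriefings can stay as they are, since Phase I results feed device improvement. What Group 2 may have learned at those debriefings is not undone, and the report should state this as a limitation.
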